After the database lock and unblinding, statistical analysis will be performed for unblinded data. Proportion of subjects with a decrease from baseline \geq RD in mean NTDT-PRO T/W score, over Weeks 13 to 24 and Weeks 37 to 48 in the luspatercept group will be compared with the placebo group. The CMH test will be used with baseline NTDT-PRO T/W category ≥ 3 versus < 3 as the stratum to compare the response rates between the 2 groups. The corresponding 95% confidence interval for odds ratio will also be provided.

9.6.3.6. FACIT-F Fatigue Subscale: Response at Weeks 13 to 24 and Weeks 37 to 48

Proportion of subjects with an increase from baseline ≥ 3 in mean FACIT-F Fatigue subscale (FS) score, over Weeks 13 to 24 and Weeks 37 to 48 in the luspatercept group will be compared with the placebo group. The CMH test will be used with baseline FACIT-F Fatigue subscale category ≥ 37 versus < 37 as the stratum to compare the response rates between the 2 groups. The corresponding 95% confidence interval for odds ratio will also be provided.

Similar analysis will be performed for Weeks 37 to 48.

9.6.3.7. SF-36 v2: Mean Change from Baseline at Week 24 and Week 48

The SF-36 Version 2.0 (acute condition with 1-week recall period) is a self-administered instrument consisting of 8 multi-item scales that assess 8 health domains: Physical functioning, Role-Physical, Bodily Pain, General Health, Vitality, Social functioning, Role-Emotional, and Mental Health. Two overall summary scores (Physical Component and Mental Component) can also be obtained.

Summary statistics for the PCS and MCS norm-based scores, as well as change from baseline in these scores, will be assessed at Weeks 12, 24, 36, and 48. Scoring for the SF-36 and methods to address missing values will be accomplished according to directions provided by the instrument developers.

A mixed effect repeated measure model will be used with subjects as the random effect. The model includes the change from baseline scores up to Week 24 and 48 as the outcome, and treatment group assignment, time, baseline scores, randomization stratification factor(s), time-by-baseline score, and time-by-treatment group assignment in the model. If any of the interaction terms are not significant, it will be excluded from the final model.

9.6.3.8. LIC / ICT: Responder Analysis at Week 24 and Week 48

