4.2.2.2. Other Secondary Efficacy Endpoints

Other secondary efficacy endpoints include:

- Mean change from baseline in mean Functional Assessment of Chronic Illness Therapy-Fatigue (FACIT-F) Fatigue Subscale (FS) score over a continuous 12-week interval from Week 13 to Week 24.
- Mean change from baseline in mean NTDT-PRO Shortness of Breath (SoB) domain score over a continuous 12-week interval from Week 13 to Week 24
- Mean change from baseline in mean hemoglobin values in the absence of transfusions over a continuous 12-week interval from Week 37 to Week 48.
- Mean change from baseline in mean FACIT-F Fatigue Subscale (FS) score, mean NTDT-PRO T/W domain score and mean NTDT-PRO SoB domain score over a continuous 12-week interval from Week 37 to Week 48.

- Proportion of subjects with an increase from baseline ≥ 3 in mean FACIT Fatigue Subscale (FS) score over a continuous 12-week interval from Week 13 to Week 24.
- Proportion of subjects with an increase from baseline ≥ 3 in mean FACIT Fatigue Subscale (FS) score over a continuous 12-week interval from Week 37 to Week 48.
- Mean change from baseline in the physical component summary (PCS) and mental component summary (MCS) scores of Medical Outcomes Study 36-Item Short Form (SF-36-v2) at Week 24 and Week 48.
- Proportion of subjects with improvement of iron overload at Week 24 and Week 48, as measured by:
 - For subjects with baseline liver iron concentration (LIC) (by magnetic resonance imaging [MRI]) ≥ 3 mg/g dry weight (dw): $\geq 20\%$ reduction in LIC, OR $\geq 33\%$ decrease in iron chelation therapy (ICT) daily dose
 - For subjects with baseline LIC (by MRI) < 3 mg/g dw: no increase in LIC > 1 mg/g dw AND not starting treatment with ICT or no increase in ICT daily dose $\geq 33\%$, if on ICT at baseline.
- Mean change from baseline in serum ferritin at Week 24, Week 48, and up to last assessment.
- Mean change from baseline in LIC at Week 24, Week 48, and up to last assessment.
- Proportion of subjects who are transfusion-free over 24 weeks.
- Proportion of subjects who are transfusion-free over 48 weeks.
- Duration of the mean hemoglobin increase from baseline ≥ 1.0 g/dL.
- Mean change from baseline in the 6MWT distance at Week 24 and Week 48.
- Proportion of subjects who have an increase from baseline ≥ 1.5 g/dL in mean of hemoglobin values over a continuous 12-week interval from Week 13 to Week 24 in the absence of transfusions.

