5. GENERAL STATISTICAL CONSIDERATIONS

5.1. Reporting Conventions

Summary tables, listings, figures and any supportive SAS outputs will include a “footer” of explanatory notes that will indicate, at a minimum, the following:

- Program source (e.g., SAS program name, including the path, that generates the output) and
- Data extraction date (e.g., the database lock date, run date)

The purpose of the data extraction date is to link the output to a final database, either active or archived, that is write-protected for replication and future reference. An output date will also appear on each output page and will indicate the date the output was generated by the analysis program.

The following reporting conventions apply generally to tables, listings, and figures:

- Data from all study centers will be combined for analysis;
- The randomization stratification variables used in the analyses will be derived based on the electronic case report form (eCRF) data.
- All statistical tests of the treatment effect will preserve a significance level of 0.050 for 2-sided tests. Testing of interactions will be performed at the 0.100 significance level, unless specified otherwise;
- P-values will be rounded to 4 decimal places. P-values that round to 0.0000 will be presented as ‘<0.0001’ and p-values that round to 1.000 will be presented as ‘>0.9999’;
- Confidence intervals (CIs) will be presented as 2-sided 95% CIs unless specified differently in specific analysis;
- Summary statistics will consist of the number and percentage of subjects in each treatment group for discrete variables, and the sample size, mean, median, Standard Deviation (SD), Q1, Q3, minimum, and maximum for continuous variables;
- All mean, median, Q1, and Q3 values will be formatted to one more decimal place than the measured value. Standard deviation values will be formatted to two more decimal places than the measured value; Minimum and maximum values will be presented to the same number of decimal places as the measured value.
- All percentages will be rounded to one decimal place. The number and percentage of responses will be presented in the form XX (XX.X%), where the percentage is in the parentheses; when the number of a response is zero, percentage will not be presented for that response;
- All listings will be sorted for presentation in order of treatment group, study center, subject, and date of procedure or event if not otherwise specified;

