Scores for each domain and composite summary scale of the SF-36 will be derived using the Quality Metric's Health Outcomes™ Scoring Software 5.1, a software designed to provide standardized scoring methods for the SF-36 based on the 2009 US general population normative data (*Maruish, 2011*). The scoring algorithm, using the 1998 US general population normative data as an example, for the SF-36 is shown in Appendix 18.3.3.

Summary statistics (n, mean, median, SD, range) for PCS and MCS norm-based scores along with the change from baseline will be summarized at Weeks 12, 24, 36, and 48 for each treatment group. The Norm-base scores will be used for domain analysis and the PCS analysis. The raw scores for each individual question and the calculated domain and component scores will be presented in the listings for SF-36.

A mixed effect repeated measure model will be used with intercept and time as the random effect. The model includes the change from baseline scores up to Week 48 as the outcome, and treatment group assignment, time (weeks since Dose 1 Day 1), baseline scores, randomization stratification factor(s), time-by-baseline score, and time-by-treatment group assignment terms in the model. The unstructured covariance matrix will be used to obtain the random effects variance components.

If the MMRM model using an unstructured covariance matrix fails to converge with the default Newton-Raphson algorithm, the Fisher scoring algorithm or another appropriate method will be used to provide initial values of the covariance parameters. In the rare event that none of the above methods yields convergence, a structured covariance, such as heterogeneous Toeplitz and Toeplitz structures, will be used to model the correlation among repeated measurements. In this case, the empirical option will be used because the sandwich variance-covariance estimator is asymptotically consistent.

To assess the extent of missing data at each assessment visit by treatment group, compliance rates for the SF-36 will be estimated on the ITT population separately based on the number of subjects included in the ITT population per treatment group who are eligible for assessment at a given scheduled visit. Subjects will be considered compliant with completion of the SF-36 assessment if at least half of the 36 items (i.e., ≥ 18 items) are completed.

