14 HEALTH RELATED QUALITY OF LIFE ANALYSIS

The HRQoL analyses are addressed in corresponding subsection in Section 10.4. This SAP only provides description of main HRQoL analysis specify in the protocol. A detailed statistical analysis of HRQoL data will be provided in a separate HRQoL SAP, which will be finalized prior to database lock. The HRQoL SAP will be appended to separate specific HRQoL report.

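### Protocol 9.6.3.7 drops non-significant interaction terms from the SF-36 model, but SAP 10.4.6 lists them with no deletion step; the protocol rule would replace the Week 24 and Week 48 differences with an average over visits

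*Protocol*

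**What the plan says.** The endpoint is visit-specific. SAP 4.2.2.2, in line with Protocol Table 2, defines it as mean change in the PCS and MCS "scores of Medical Outcomes Study 36-Item Short Form (SF-36-v2) at Week 24 and Week 48".

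The two documents model it differently:

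- **Protocol 9.6.3.7.** "A mixed effect repeated measure model will be used with subjects as the random effect". On the horizon: "The model includes the change from baseline scores up to Week 24 and 48 as the outcome". The terms include time-by-baseline and time-by-treatment. The section closes: "If any of the interaction terms are not significant, it will be excluded from the final model". It gives no significance level for that decision.
- **SAP 10.4.6.** "A mixed effect repeated measure model will be used with intercept and time as the random effect". There is one horizon, to Week 48, and the terms end with "time-by-baseline score, and time-by-treatment group assignment terms in the model". There is no deletion step and no remark that the protocol's step has been dropped.

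Two other places bear on this. SAP 5.1 sets a default: "Testing of interactions will be performed at the 0.100 significance level, unless specified otherwise". SAP 14 says of itself: "This SAP only provides description of main HRQoL analysis specify in the protocol". Both SAP 10.4.6 and SAP 14 leave further detail to a separate HRQoL SAP, which is not among the documents.

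**The concern.** Time-by-treatment is the only listed term that lets the difference between arms vary by visit. Once it is removed, the model holds a single treatment coefficient, and no Week 24 or Week 48 difference can be estimated from it. What is reported for those weeks is an average over the visits in the model: one average for both weeks if one model is fitted, or one per horizon if the protocol means two models.

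The rule treats a non-significant interaction as evidence that the effect is constant, in a trial not sized to detect that interaction. If the effect fades, a benefit seen only early can be reported as a Week 48 benefit. If it grows, the Week 48 benefit is understated. The choice of model also rests on the same outcome data, and the final confidence interval makes no allowance for that.

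Deleting time-by-baseline does not by itself remove the visit-specific treatment contrast. The time-by-treatment term is the one that matters here.

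**Working it through.** **The plan's own figure.** The documents state no power, SD or correlation for SF-36, so only the sample size and alpha can be checked, through the NTDT-PRO T/W power in Protocol 9.3. The standardised difference is 0.7 / (1.2 × √(1/100 + 1/50)) = 0.7 / 0.2078 = 3.37, and Φ(3.37 − 1.96) = 92%, against the stated 91%. The inputs 100/50 and two-sided 0.05 are confirmed.

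**Inputs from the documents.** 100 vs 50 subjects; SF-36 every other dose, about every 6 weeks, hence 8 post-baseline visits at Weeks 6 to 48; treatment test at two-sided 0.05; interaction test at 0.10 by the SAP 5.1 default, with 0.05 also run because the protocol gives no level.

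**Assumed, not in the documents.** Random-intercept SD 5; residual SD 4; random-slope SD 0 (intercept only) or 0.05, 0.08, 0.12 per week, uncorrelated with the intercept; complete data; variances known; time linear; true difference A(1 − t/48), which is exactly 0 at Week 48. Total SD at Week 48 with random slopes is √(25 + 16 + 48² × slope SD²), or 6.8 to 8.6.

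**What deletion does to the estimate.** With a random intercept and balanced visits, the common-effect estimate is the plain mean over visits. The mean visit week is 27, so its expectation is A(1 − 27/48) = 0.4375A: 0.875 for A = 2 and 1.31 for A = 3. The true Week 48 value is 0.

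**One case by hand** (random intercept, A = 2, interaction at 0.05). The variance factor is 1/100 + 1/50 = 0.03.

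- Interaction slope: −2/48 = −0.0417. Its SE is √(0.03 × 16 / 1512) = 0.0178, where 1512 = Σ(t − 27)². So z = −2.34, and P(not significant) ≈ Φ(1.96 − 2.34) = 0.35.
- Common effect: SE = √(0.03 × (25 + 16/8)) = 0.90, so z = 0.875/0.90 = 0.97 and P(significant) = 0.163.
- The two estimates are independent in this model, so the deleted branch contributes 0.35 × 0.163 = 5.8 points.
- The retained branch tests the Week 48 contrast, with SE √(0.81 + 21² × 0.0178²) = 0.975. It adds about 3.0 points.
- Total: about 8.8%, against 5% if the term is always kept.

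**The full grid.** Percentage of trials rejecting a true Week 48 null, from 1,000,000 draws of the joint normal distribution of the slope, Week 48 and common-effect estimates:

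| Interaction level | A | Intercept only | Slope SD 0.05 | 0.08 | 0.12 |
|---|---|---|---|---|---|
| 0.05 | 2 | 8.8 | 12.3 | 17.6 | 25.6 |
| 0.05 | 3 | 6.2 | 8.7 | 14.4 | 27.0 |
| 0.05 | 4 | 5.1 | 5.5 | 7.4 | 15.3 |
| 0.10 | 2 | 7.4 | 10.0 | 14.3 | 21.5 |
| 0.10 | 3 | 5.6 | 6.9 | 10.4 | 19.8 |
| 0.10 | 4 | 5.0 | 5.2 | 6.0 | 10.5 |

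With the term kept, every cell is 5.0. Random slopes raise the rate in two ways. The interaction is harder to detect: for A = 2 at 0.05 it is missed 35% of the time with intercept only and 67% at slope SD 0.12. The common-effect estimate also puts more weight on early visits, so its expectation rises from 0.875 to 1.52.

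For A = 2-3 with random slopes at 0.05, coverage of the 95% interval for Week 48 is 73-91%. If the effect instead grows linearly to 2 points at Week 48, the rule reports 1.3-1.7 on average and loses about 4-6 points of power.

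**Other shapes.** A separate calculation used 90 vs 45, a random intercept, correlation 0.5 or 0.7, 4 or 8 visits, early effects of 0.2-0.4 SD and three waning profiles. It gave about 5% to 52% under the rule, the top coming from an effect that is constant until the last visit and then vanishes. Keeping the interaction with categorical time gave 4.7-5.5% throughout. Keeping it with linear time gave up to about 11% (4 visits) or 33% (8 visits) when the true effect was not linear.

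**The case against.** The strongest reply is that the SAP has already settled this. Protocol 9.2 leaves detailed analysis rules to the SAP. SAP 10.4.6 rewrites the protocol paragraph, with new random effects, a single horizon and covariance fallbacks, and leaves out the deletion sentence. SAP 10.4.18 uses the same form of model for hemoglobin, also without deletion. Read alone, the SAP analysis does not have this fault, and that part stands. But the omission is silent, SAP 14 presents the SAP as describing the protocol's analysis, and the document that is to hold the detail is not available. An analyst could follow either text.

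Second, the larger error rates pair the protocol's deletion rule with the SAP's random slopes, a combination that neither document specifies. This also stands. With the protocol's random subject effect, read as a random intercept, the excess in these scenarios is at most about 4 points, and less at the 0.10 level.

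Third, the consequence is bounded. Descriptive PCS and MCS changes at Weeks 12, 24, 36 and 48 are reported by arm in any case, so marked fading would be visible.

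A reader might go further and infer that one inflated error rate belongs to the plan. It does not: every figure above needs an assumed early effect that reaches exactly zero at Week 48 and assumed variances. With no effect at any visit, selection alone gives about 5-7%. A reader might also tie Week 48 to the long-term objective, but the documents use that phrase for hemoglobin only. The Week 48 SF-36 comparison rests on the endpoint definition itself.

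**Conclusion.** The point holds as a protocol-SAP discrepancy with a real statistical consequence if the protocol text is followed. The protocol rule replaces the stated Week 24 and Week 48 differences with an average over visits whenever the interaction is not significant. This biases the Week 48 estimate and its test when the effect changes over time.

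Under the assumptions listed, with a 2-3 point effect fading linearly to zero, a true Week 48 null is rejected about 6-9% of the time with a random intercept only and about 9-27% with random slopes at interaction level 0.05 (about 7-22% with random slopes at 0.10), against 5% with the term kept. Steeper fading gives less, because the interaction is then usually detected. These figures illustrate the mechanism; they do not predict this trial.

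The documents do not support extending this to the trial's controlled error rate. SF-36 is an other secondary endpoint outside the sequence in SAP 10.1, so the primary and key secondary tests are unaffected. Nor do they settle that Weeks 24 and 48 collapse into a single test: the protocol's wording of the horizon also allows two models.

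**What to change.** Delete the closing sentence of Protocol 9.6.3.7. State in SAP 10.4.6, and carry into the HRQoL SAP, that time-by-treatment and time-by-baseline are retained whatever their p-values, and that the Week 24 and Week 48 differences are estimated as contrasts from that model. Preferably specify visit as a categorical factor: SAP 10.4.6 describes time as weeks since the first dose, and a linear time term can still misstate Week 48 when the effect is not linear in time.

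The cost is one deleted sentence and one added clause. If the effect is truly constant over time, the Week 24 and Week 48 intervals are slightly wider than under a common-effect model. If the SAP model was the intended one, retaining the terms only confirms it in writing.

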9.6.3.11. Transfusion Free for 24 and 48 weeks

Proportion of subjects who receive no RBC transfusions from Week 1 to Week 24 will be compared between the 2 treatment groups using CMH test with randomization stratification factor(s) adjusted.

Similarly, proportion of subjects who receive no RBC transfusion from Week 1 to Week 48 will be compared between the 2 treatment groups using CMH test with stratification factor(s) adjusted.

9.6.3.12. Duration of Mean Hemoglobin Increase from Baseline ≥ 1.0 g/dL

Descriptive statistics will be generated for the duration of mean hemoglobin increase for each treatment group. Kaplan-Meier method will be used for censored subjects. No statistical test will be performed to compare the 2 groups.

The duration will start from the first day of the first rolling 12-week window that achieves mean Hb increase from baseline ≥ 1.0 g/dL. It will end with the last day of the last consecutive rolling 12-week window that maintains mean Hb increase from baseline ≥ 1.0 g/dL.

9.6.3.13. 6MWT: Mean Change at Week 24 and 48

Mean changes from baseline at Weeks 24 and 48 will be analyzed using ANCOVA method with treatment group and randomization stratification factor(s) in the model and baseline 6MWT value as the covariate. In addition, subgroup of subjects with baseline 6MWT ≤ 450 meter will be performed.

Mean changes from baseline at Week 48 will be analyzed similarly.

9.6.3.14. Proportion of Mean Hemoglobin Increase From Baseline ≥ 1.5 g/dL at Week 13 to 24

Similar to the primary efficacy analysis, the proportion of subjects who have an increase from baseline ≥ 1.5 g/dL in mean of hemoglobin values over a continuous 12-week interval from Week 13 to Week 24 will be performed on the ITT population. Cochran-Mantel-Haenszel (CMH) test will be performed with randomization stratification factor(s) in the model to compare the treatment and placebo groups at 2-sided 0.05 level.

9.7. Safety Analysis

All safety analyses will be performed on the safety population. Full details will be included in the SAP. Planned data presentations and analyses include the following:

- Adverse events will be coded using MedDRA. Adverse event listings will include the verbatim term and the MedDRA preferred term. Treatment-emergent adverse events will be summarized by system organ class and preferred term. Treatment-emergent adverse events leading to death or to discontinuation from treatment, TEAEs classified as NCI CTCAE (version 4.0) all grades or grade 3/4 TEAEs, related to investigational product, and serious TEAEs will be summarized separately.
- Clinical laboratory results will be summarized descriptively by treatment group. Clinically significant hematologic and non-hematologic laboratory abnormalities will be listed and summarized according to the NCI CTCAE by treatment group.
- Physical examination data and vital sign measurements, including body weight, will be listed for each subject at each visit. Descriptive statistics for vital signs, both observed values and changes from baseline, will be summarized by treatment group.

9.8. Interim Analysis

No Interim analysis is planned.

9.9. Timing of Analyses

9.9.1. Primary Clinical Study Report

Clinical study report (CSR) will include safety and efficacy parameters with a cut-off date at the time when all subjects enrolled in the DBTP have completed 48 weeks in the study or discontinued earlier (ie, at the time of the unblinding of the study, whichever occurs later). Thus, the primary and secondary analysis will be conducted after all required information is available for these endpoints (ie, after all subjects have completed 48 weeks in the study or discontinued earlier). With this cut-off date and upon the data base lock the study will be unblinded.

9.9.2. Final Clinical Study Report

The final CSR will include efficacy and safety data at the time of the End of the Trial (EOT definition in Section 3.3).

The final analyses will be conducted on efficacy and safety endpoints as applicable after Week 48.

9.10. Other Topics

9.10.1. Pharmacokinetic Analysis

Population PK analysis will be performed using nonlinear mixed effect modeling. Concentration data obtained from this study and other studies will be combined to develop a population PK model that describes the PK exposure data and the associated variability. Subject-specific factors (demographics, baseline characteristics, markers for organ function, anti-luspatercept antibodies,

etc.) will be explored as covariates for their potential to influence luspatercept PK parameters. Empiric individual Bayesian estimates of PK parameters will be generated using the final population PK model. With these individual parameter estimates and appropriate measures of luspatercept exposure (AUC, maximum concentration of drug [C_{max}], or other exposure metrics of interest) will be computed for each subject.

The relationship between serum luspatercept exposure and the selected efficacy/safety endpoints or biomarkers of interest will be explored as appropriate.

[REDACTED]

